1.2.5. NRTI Retreatment

It is recommended that NRTI therapy be reinitiated in participants during the Follow-Up Period if they meet any of the following criteria:

- HBV DNA increase $\geq 2 \log_{10}$ IU/mL within a 2-week period
- HBV DNA $> 100,000$ IU/mL at any Follow-Up Period visit (regardless of other biochemical parameters or ALT values)
- Confirmed increase of HBV DNA $> 20,000$ IU/mL (i.e., at 2 consecutive collections, regardless of other biochemical parameters or ALT values)
 - Note: The repeat HBV DNA test should be performed as soon as possible and no later than 7 calendar days after the initial result is received. Central laboratory testing is preferred, but local laboratory results will be accepted if it is not feasible to collect central laboratory results in time.

- HBV DNA > 2,000 IU/mL concurrent with any of the following criteria at the same visit:
 - Confirmed total bilirubin > 2x ULN and ALT > ULN
 - Any sign of hepatic decompensation (including, but not limited to, confirmed increase in prothrombin time [PT] ≥ 2 or international normalized ratio [INR] ≥ 0.5 from baseline, jaundice, ascites, encephalopathy, etc.)
 - ALT > 10x ULN
 - ALT > 2x ULN persisting for ≥ 12 consecutive weeks
 - ALT > 5x ULN persisting for ≥ 4 consecutive weeks
- Confirmed HBeAg seroreversion (i.e., HBeAg positive after being HBeAg negative at NRTI discontinuation)
- Any other clinically significant event(s) warranting initiation of NRTI therapy in the opinion of the investigator after discussion with the Sponsor

Participants who are retreated with NRTI therapy should continue to be followed per the SOA for the Follow-Up Period through the Week 48 visit. Participants with HBV DNA increase $\geq 2 \log_{10}$ IU/mL within a 2-week period should:

[figure not shown]
[figure not shown]
- return to the site for an unscheduled visit to measure HBV DNA levels and liver function tests as soon as possible after the investigator becomes aware of the HBV DNA increase
- continue returning weekly until HBV DNA levels stabilize (do not increase $\geq 1 \log_{10}$ IU/mL over a 4-week period or start decreasing for at least 2 consecutive visits), after which they should continue per the SOA for the Follow-Up Period

If any unscheduled visits needed as outlined above coincide with an existing visit per the Follow-Up Period SOA, then the Follow-Up visit assessments should be conducted.

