3. ANALYSIS SETS

For the purposes of analysis, the participant analysis sets are defined in **Table 4**.

Table 4: Participant Analysis Set

Participant Analysis Set	Description
All Enrolled Set	The All Enrolled Set includes all participants who signed the informed consent form and were assigned to study intervention. Summaries for disposition, demographics and baseline characteristics will be reported based on the All Enrolled Set.
Full Analysis Set (FAS)	The FAS includes all participants in the All Enrolled Set who received at least one dose of study intervention(s). This set is the primary endpoint analysis set for efficacy and antiviral analyses. Participants will be analyzed according to the study intervention assigned.
Safety Analysis Set	The Safety Analysis Set includes all participants who received any amount of study intervention. All safety analyses will be based on the Safety Analysis Set. Participants will be analyzed according to the study intervention received.
PK Analysis Set	The PK Analysis Set includes all participants in the FAS who had at least one measurable post-dose concentration. The PK Analysis Set will be used for all PK analyses.
Immunogenicity Analysis Set	The Immunogenicity Analysis Set includes all participants in the FAS who had pre-dose and at least one post-dose measurement of immunogenicity, including screening, titers, or neutralizing characterization, as applicable. The Immunogenicity Analysis Set will be used for analyses of the immunogenicity endpoints.

For the efficacy endpoints, no participants in the FAS will be excluded from the efficacy analysis.

Three interim analyses (IAs) will be conducted for each cohort to evaluate the efficacy endpoints at Week 24, EOT, and 24 weeks post-EOT when all participants in the cohort have completed the respective visits. All participants who enrolled or received any amount of study intervention prior to the data cutoff date will be in the scope of the IAs. All data reported on or before the data cutoff date will be included in the IAs. The participant analysis sets for IAs are defined in **Table 5**.

Table 5: Interim Analysis Set

Participant Analysis Set	Description
Interim Full Analysis Set 1 (iFAS1)	The iFAS1 will include participants in the FAS whose scheduled Week 24 Visit is before or on the IA1 data cutoff date.

	This set also includes the FAS participants who prematurely discontinued the study intervention prior to the IA1 data cutoff date.

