
9. Proportion of participants achieving sustained suppression of HBV DNA (< LLOQ) with HBsAg loss (< 0.05 IU/mL) after discontinuation of all treatment:
 
a. at 24 weeks
 
b. at the F48 Follow-Up visit
 
11. Proportion of participants achieving sustained suppression of HBV DNA (< LLOQ) after discontinuation of all treatment:
 
a. at 24 weeks
 
b. at the F48 Follow-Up visit
	
Due to early study termination, modification to timepoints of a. and b. as below:
 
a) at 24 weeks after discontinuation of all treatments (an analysis window of 168 ± 14 days will be applied to capture data around the 24 weeks timepoint, following the rules in Appendix 2 for data selection)
 
b) at the last Follow-Up visit, for participants who have > 24 weeks of discontinuation, after discontinuation of all treatments
 
c) at the last Follow-Up visit after discontinuation of all treatments (all participants will be included in the denominator)
 
Specifically, for a) and b), the denominator used in the percentage calculation will exclude participants with uncertain NRTI discontinuation status due to early study termination (e.g., no Follow-Up 12 visit).
 
The number and percentage of participants achieving
 
 • sustained suppression of HBV DNA (< LLOQ) • sustained suppression of HBV DNA (< LLOQ) with HBsAg loss (< 0.05 IU/mL) 
will be summarized by cohort with the two-sided 95% Clopper-Pearson CI.
 
In addition, the number and percentage of participants achieving
 
 • sustained suppression of HBV DNA (< LLOQ), allowing transient viremia

	
 • sustained suppression of HBV DNA (< LLOQ) with HBsAg loss (< 0.05 IU/mL), allowing transient viremia where transient viremia is defined as HBV DNA \geq LLOQ or HBsAg \geq LLOQ for \leq 35 days, adapted from the 2022 American Association for the Study of Liver Diseases (AASLD) – The European Association for the Study of the Liver (EASL) functional cure definition (AASLD-EASL, 2022), will be analyzed similarly. 
Similarly, the analyses above will be repeated after replacing “HBsAg loss (<0.05 IU/mL) with “HBsAg < 100 IU/mL”. Accordingly, the transient viremia is defined as HBV DNA \geq LLOQ or HBsAg \geq 100 IU/mL for \leq 35 days, adapted from the 2022 AASLD-EASL partial functional cure definition (AASLD-EASL, 2022).

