4.10.1. Modifications to the Approved Study Protocol

Protocol	SAP v2.0

Section 3: secondary endpoints:
 
9. Proportion of participants achieving sustained suppression of HBV DNA (< LLOQ) with HBsAg loss (< 0.05 IU/mL) after discontinuation of all treatment:
 
 a. at 24 weeks b. at the F48 Follow-Up visit 
11. Proportion of participants achieving sustained suppression of HBV DNA (< LLOQ) after discontinuation of all treatment:
 
 a. at 24 weeks b. at the F48 Follow-Up visit 	
A modification to the timepoint is below due to early study termination:
 
 a. at 24 weeks post-stopping all treatments b. at the last Follow-Up visit, for participants who have > 24 weeks of discontinuation post-stopping all treatments c. at the last Follow-Up visit 
Add additional analysis below:
 
In addition, the number and percentage of participants achieving

	
 • sustained suppression of HBV DNA (< LLOQ), allowing transient viremia after discontinuation of all treatment • sustained suppression of HBV DNA (< LLOQ) with HBsAg loss (< 0.05 IU/mL), allowing transient viremia after discontinuation of all treatment 
where transient viremia is defined as HBV DNA \geq LLOQ or HBsAg \geq LLOQ for \leq 35 days, adapted from the 2022 American Association for the Study of Liver Diseases (AASLD) – The European Association for the Study of the Liver (EASL) functional cure definition (AASLD-EASL, 2022), will be analyzed similarly.
 
The analyses above will be repeated after replacing “HBsAg loss (<0.05 IU/mL) with “HBsAg < 100 IU/mL”. Accordingly, the transient viremia is defined as HBV DNA \geq LLOQ or HBsAg \geq 100 IU/mL for \leq 35 days.

Master protocol Section 9.3: All Screened Set includes all participants who signed the informed consent form.	All Screened Set will not be included in this SAP. Because the All Screened Set will not be used in the analysis. Instead, the number of participants screened will be provided in the disposition table.

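### SAP 4.4.1, endpoints 9 and 11: the denominator of timepoint b), which replaces the F48 reading, is not fixed, and one natural reading selects on achieved time off treatment and would overstate durability

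*SAP*

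**What the plan says.** The SAP covers the STRIVE sub-study. In its section 1.1 (Table 1), endpoints 9 and 11 are the proportions with sustained HBV DNA suppression, with and without HBsAg loss, after all treatment has stopped, read at 24 weeks and at F48.

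Section 4.4.1 changes this: "Due to early study termination, modification to timepoints of a. and b. as below". Three readings follow:

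- a) at 24 weeks after stopping all treatment, with a window of 168 ± 14 days;
- b) "at the last Follow-Up visit, for participants who have > 24 weeks of discontinuation, after discontinuation of all treatments";
- the third, c), uses the same final visit, but here "all participants will be included in the denominator".

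The sentence after c) states that "for a) and b), the denominator used in the percentage calculation will exclude participants with uncertain NRTI discontinuation status due to early study termination". The example it gives is a participant with no F12 visit. Section 4.10.1 words b) slightly differently: "at the last Follow-Up visit, for participants who have > 24 weeks of discontinuation post-stopping all treatments".

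Three other rules bear on the denominator. Section 3 says "For the efficacy endpoints, no participants in the FAS will be excluded from the efficacy analysis". Section 4.1 treats missing response data as failure. Section 1.2.5 sets out when restarting is advised ("It is recommended that NRTI therapy be reinitiated in participants during the Follow-Up Period if they meet any of the following criteria") and keeps retreated participants in follow-up to Week 48.

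**The concern.** Time off treatment is partly an outcome. A participant who rebounds and restarts NRTI, or who stops and then withdraws, has failed to show sustained off-treatment suppression. If b) admits only people who achieved more than 24 weeks off, such participants are removed instead of counted as failures, and the rate is computed among those who had done well enough to remain.

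Early termination is a good reason to restrict b): a last visit a few weeks after stopping says nothing about late durability. That reason supports a restriction on how long a participant could have been followed, not on how long the participant stayed off treatment.

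At stake is the figure that takes the place of the planned F48 result. STRIVE cohorts are planned at about 10 or 15, and fewer will stop NRTI, so one or two people can change the message.

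**Working it through.** **Plan's own figure.** The SAP gives no figure for endpoints 9 or 11 at timepoint b). Its only sizing figure, Table 6, reproduces: with 15 participants, a 2% null and one-sided 0.025, rejection needs at least 3 responders (exact tail 0.0030), and power at a true 25% is 76.4%. Nothing below depends on it.

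**Who can reach 24 weeks.** NRTI may be stopped at F1 or F12 (SAP 1.2.3 and 1.2.4).

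- F1 stoppers: F24 is 24 − 1 = 23 weeks off, F28 is 27 weeks, F48 is 47 weeks.
- F12 stoppers: F36 is 36 − 12 = 24 weeks off, which at nominal timing is not more than 24; F48 is 36 weeks.

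**Readings of b).**

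1. Continuous time off NRTI must exceed 24 weeks. Early restarters and early withdrawals both leave the denominator.
2. Time from stopping to the last visit must exceed 24 weeks. The wording in 4.10.1 fits this. Restarters who stay in follow-up are kept; early withdrawals still leave.
3. The denominator is the FAS less those of uncertain NRTI status, as the sentence after c) reads. Restarters and withdrawals both stay.

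**Illustration (all counts assumed; the documents give none).** Cohort of 15; 2 of uncertain status; 6 stop all treatment more than 24 weeks before termination; 3 of the 6 are sustained responders; *e* of the other 3 restart NRTI before 24 weeks but stay in follow-up. The rate is x/n with an exact 95% Clopper-Pearson interval: lower limit the 0.025 quantile of Beta(x, n − x + 1), upper limit the 0.975 quantile of Beta(x + 1, n − x), and 100% when x = n.

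| Denominator | n | Rate | 95% CI |
|---|---|---|---|
| Reading 1, e = 1 | 6 − 1 = 5 | 3/5 = 60.0% | 14.7–94.7 |
| Reading 1, e = 2 | 6 − 2 = 4 | 3/4 = 75.0% | 19.4–99.4 |
| Reading 1, e = 3 | 6 − 3 = 3 | 3/3 = 100% | 29.2–100 |
| Reading 2, or potential follow-up | 6 | 3/6 = 50.0% | 11.8–88.2 |
| Reading 3 | 15 − 2 = 13 | 3/13 = 23.1% | 5.0–53.8 |
| Timepoint c) | 15 | 3/15 = 20.0% | 4.3–48.1 |

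If the *e* participants withdraw instead of restarting, reading 2 gives the same figures as reading 1; only a potential follow-up denominator keeps them.

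**Against the other rules.** Readings 1 and 2 remove FAS members, contrary to section 3, and turn early withdrawals into exclusions where section 4.1 would make them failures. Reading 3 agrees with the sentence after c), but leaves the 24-week phrase without a clear role. Under every reading, no rule states the outcome of a participant who restarts NRTI and is suppressed on it at the last visit.

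**The case against.** A reader might infer that the SAP removes early relapsers who restart NRTI. The documents do not say so, and the case against that inference is strong.

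- The only sentence that sets the denominator of a) and b) excludes people of uncertain NRTI status and nobody else. Such a participant did not stop at F1 and has no F12 visit, so could not have 24 weeks off. The sentence would do nothing in b) if b) were already limited to long-term stoppers. This favours a wider denominator, and it explains why c) says that everyone is included: c) brings the uncertain-status group back.
- Neither 4.4.1 nor 4.10.1 says continuously off or without retreatment. Since retreated participants stay in follow-up, time since stopping would retain them.
- Much of the wanted context is already planned. Timepoint c) gives the all-participant rate; section 4.1 summarises efficacy among TDF/TD discontinuers as well as overall; section 4.5.1 tabulates retreatment criteria and virological relapse. Early relapse would not vanish from the report.
- The endpoint is descriptive, in an exploratory study without hypothesis testing.

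All of this stands, and it limits the harm. It does not settle the wording. Section 4.4.1 uses the FAS unless otherwise specified, and the 24-week phrase can be taken as such a specification. A programmer applying it literally would filter on it. Timepoint c) is not a full substitute, because it sets no minimum time off treatment.

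**Conclusion.** The concern holds as an ambiguity that can bias the result. The 24-week phrase in b) can be applied as a filter on achieved time off treatment. Early withdrawals would then be lost, as would restarters if continuous time off is meant, and the rate would overstate durability. That use would conflict with section 3, with missing equals failure, and with the sentence naming only uncertain status as an exclusion.

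The stronger conclusion, that b) is survivor-biased by design, is not supported: removal of restarters is one reading and not a stated rule. With the all-participant rate available in c), this should be fixed but is not critical.

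On the assumed counts, b) runs from 23.1% to 100% across readings. Dropping 1, 2 or 3 early restarters moves it from 50% to 60%, 75% or 100%. The actual size depends on how many participants stopped NRTI and what followed. The supplied protocol is for THRIVE, which has no F1/F12 stopping rule, and cannot resolve the wording.

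**What to change.** In SAP 4.4.1 and 4.10.1, state the denominator of b) once, by potential follow-up: all participants who stopped all treatment more than 24 weeks before the study termination date, whatever happened afterwards. Define the 24 weeks as time from stopping to that date. Count NRTI restart, rebound or missing data as failure in the main analysis; the separate analysis that allows transient viremia keeps its own 35-day tolerance. Present b) beside the all-participant rate from c), with numerators and denominators shown. Add to section 3 that b) is a stated exception to the FAS rule.

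The cost is SAP wording and the matching table programming; no new data are needed. The reported percentage may be lower than under a literal filter.

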1.2. Study Design

1.2.1. Overall Design

STRIVE is a Phase 2, multi-center, open-label study designed to evaluate the safety and efficacy of regimens containing VIR-3434, VIR-2218, PEG-IFN α , and NRTI (TDF/TD)¹ in non-cirrhotic adult participants with chronic HBV infection who have not received prior NRTI or PEG-IFN α treatment. The study is planned to be conducted at multiple clinical investigative sites globally.

The STRIVE sub-study is intended to evaluate up to 48-week regimens of VIR-3434 and NRTI, VIR-3434 and NRTI in combination with VIR-2218, and VIR-3434 and NRTI in combination with both VIR-2218 and PEG-IFN α in participants with chronic HBV infection. Study populations II and III in [Table 2](#) as defined in the Master Protocol will be included in this sub-study. Participants who have not received any prior NRTI treatment will be eligible for enrollment into this sub-study.

Table 2: Study Population

Master Protocol Population	HBeAg Status	HBV DNA Level	ALT Level
II	Positive	> 2,000 IU/mL	> ULN and $\leq 5 \times$ ULN

¹ In STRIVE, NRTI refers to Tenofovir disoproxil fumarate dose (TDF) or Tenofovir disoproxil (TD). TDF will be supplied in the United States, TD will be supplied outside the United States.

III	Negative	> 2,000 IU/mL	> ULN and \leq 5x ULN
-----	----------	---------------	-------------------------

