1.2.3. Intervention Groups and Duration

There are 5 cohorts planned in this sub-study.

Table 3: Intervention Groups

Cohort	Study Drug	Dose	Route	Number of Doses	Frequency of Dosing
1a	VIR-3434	300 mg	SC	12	Every 4 weeks
	TDF	300 mg ^b	Oral	\geq 308 ^c	Every day
2a	VIR-3434	Up to 300 mg ^a	SC	12	Every 4 weeks
	TDF	300 mg ^b	Oral	\geq 308 ^c	Every day
3a	VIR-3434	300 mg	SC	4-6 ^d	Every 8-12 weeks ^d
	TDF	300 mg ^b	Oral	\geq 252 ^c	Every day
4a	VIR-3434	300 mg	SC	12	Every 4 weeks
	VIR-2218	200 mg	SC	12	Every 4 weeks
	TDF	300 mg ^b	Oral	\geq 308 ^c	Every day
5a	VIR-3434	300 mg	SC	13	Every 4 weeks
	VIR-2218	200 mg	SC	13	Every 4 weeks
	PEG-IFN α	180 mcg	SC	48	Every week
	TDF	300 mg ^b	Oral	\geq 336 ^c	Every day

^a The dose of VIR-3434 will be determined before participants are enrolled in the cohort.

^b Tenofovir disoproxil fumarate dose (TDF) will be 300 mg as approved by the FDA. Supply outside the United States may be Tenofovir disoproxil (TD) 245 mg.

^c The minimum number of doses received by participant. Participants will continue receiving additional doses of TDF until they qualify for NRTI discontinuation.

^d The dosing regimen will be finalized before participants are enrolled in the cohort.

The total duration in the study for participants will be up to 100 weeks in cohorts 1a, 2a, and Cohort 4a, 92-96 weeks for Cohort 3a, and 104 weeks for Cohort 5a. This includes a Screening Period (up to 56 days or 8 weeks), Treatment Period (44 weeks for cohorts 1a and 2a, 36 or

40 weeks for Cohort 3a, 44 weeks for Cohort 4a, and 48 weeks for Cohort 5a) and a Follow-Up Period (up to 48 weeks) for all cohorts.

Once participants complete the Treatment Period per their respective cohort, they will enter the Follow-Up Period. Participants will discontinue the NRTI at the F1 or F12 visit in the Follow-Up Period if they meet the criteria to discontinue NRTI ([Section 1.2.4](#)) based on the data available. Additional study visits are required for participants who discontinue NRTI in the Follow-Up Period as indicated in the SOA in the study protocol. Participants who discontinue NRTI at F1 visit will be required to return to the site for additional visits at F2, F6, F10, F28, F32, F40, and F44. Participants who discontinue NRTI at F12 visit will be required to return to the site for additional visits at F14, F18, F22, F28, F32, F40, and F44.

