4. STATISTICAL ANALYSES

4.1. General Considerations

All analyses will use SAS version 9.4 or higher. The schedule of study assessments and time points are provided in the current PREVAIL master protocol and STRIVE sub-study.

Data will be provided in by-participant listings for the All Enrolled Set, unless otherwise specified.

Efficacy endpoints will be summarized by TDF/TD discontinued (participants who discontinued TDF/TD when the TDF/TD discontinuation criteria were met in the Follow-up period) and overall for each cohort.

Continuous variables will be summarized using the following descriptive summary statistics: the number of participants (n), mean, standard deviation (SD), median, Q1 (first quartile), Q3 (third quartile), minimum value (min), and maximum value (max), unless otherwise specified. In general, the precision of the measurement for each continuous variable will be used to determine the number of decimal places to present in tables, figures, and derived listings. Minimum and maximum values will be reported with the same precision as the units of measure. The mean and median will be reported to 1 additional decimal place, and the SD will be reported to 2 additional decimal places. Any values that require transformation to standard units (metric or SI) will be converted with the appropriate corresponding precision.

Categorical variables will be summarized using counts and percentages. Percentages will be rounded to one decimal place, except 100% will be displayed without any decimal places, and percentages will not be displayed for zero counts.

Baseline value: Unless otherwise specified, the baseline value will be defined as the most recent non-missing (scheduled or unscheduled) measurement collected prior to the initial administration of study intervention. If baseline cannot be determined due to missing data, no derivation will be performed, and baseline will be set to missing.

Change (absolute change) from baseline will be calculated as post-baseline value – baseline value.

Study day: The study day of an event/measurement is defined as the relative day of the event/measurement starting with the date of the first study drug administration (reference date) as Day 1 (there will be no Day 0).

The study day of event/measurement occurring before the first study drug administration will be calculated as:

$$\text{Study Day} = (\text{Date of event/measurement} - \text{Date of first study drug administration})$$

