4.4. Secondary Endpoints Analysis

4.4.1. Secondary Efficacy Endpoints

The analysis of the following secondary endpoints will be conducted based on the FAS, unless otherwise specified. The numbering in the table below is consistent with the numbering of the endpoints in [Table 1](#). HBeAg, anti-HBsAg, and anti-HBeAg values will be provided in a by-participant listing.

Secondary Endpoints	Analysis Methods

 2. Proportion of participants with serum HBsAg ≤ 10 IU/mL at the EOT 3. Proportion of participants with serum HBsAg ≤ 10 IU/mL at 24 weeks post-EOT 8. Proportion of participants with HBsAg loss with anti-HBs seroconversion at EOT and at 24 weeks post-EOT 10. Proportion of participants achieving HBsAg loss (< 0.05 IU/mL) 
 a. at EOT b. at 24 weeks post-EOT 	
The number and proportion of participants for each endpoint will be summarized at each visit by cohort, and the two-sided 95% Clopper-Pearson CI will be calculated for each cohort.

 4. Serum HBsAg levels and change from baseline across timepoints in the study 5. Serum HBsAg level at nadir during the study 14. Mean change in serum HBsAg level from baseline across timepoints in the study 	
The observed values and the absolute change from baseline values in both IU/mL and \log_{10} IU/mL of HBsAg
 
at each visit up to end of study (EOS)
 
at nadir during the study
 
will be summarized using descriptive statistics (n, mean, SD, median, Q1, Q3, min, max) by cohort.
 
In addition, the change from baseline in \log_{10} IU/mL at each visit will be plotted for each participant by cohort.
 
Absolute value in \log_{10} IU/mL at each visit will be plotted for each participant by cohort.
 
Mean change from baseline in \log_{10} IU/mL at each visit will be plotted for each cohort.

6. Time to achieve nadir of serum HBsAg during the study
 
7. Time to achieve serum HBsAg loss (< 0.05 IU/mL)
	
Time-to-nadir of serum HBsAg during the study period (up to EOS) will be summarized as a continuous variable by cohort.
 
Time-to-HBsAg loss will be summarized as a continuous variable by cohort.

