12. For HBeAg-positive participants: proportion of participants with HBeAg loss (undetectable HBeAg) and/or anti-HBe seroconversion	
The number and percentage of participants achieving
 
 • HBeAg loss (undetectable HBeAg) will be summarized at each visit up to EOS by cohort for each visit; and • Anti-HBe seroconversion • HBeAg loss (undetectable HBeAg) and anti-HBe seroconversion will be summarized at each follow-up visit by cohort up to EOS. The two-sided 95% Clopper-Pearson CI will also be calculated at each follow-up visit for each cohort. 
The percentage will be based on those participants who have HBeAg tested positive at baseline in the FAS.

15. Proportion of participants achieving HBV DNA < LLOQ across timepoints in the study	
The number and percentage of participants with
 
 • HBV DNA < LLOQ • ALT \leq ULN

16. Proportion of participants achieving ALT \leq ULN across timepoints in the study	
will be summarized at each visit by cohort. The two-sided 95% Clopper-Pearson CI will also be calculated across visits for each cohort.
 
In addition, the individual ALT (U/L) value at each visit will be plotted for each participant by cohort.

--	---

- The LLOQ for HBV DNA is 20 IU/mL.
- HBsAg loss is defined as HBsAg < 0.05 IU/mL.
- Anti-HBs seroconversion: Anti-HBs change from baseline negative to post-baseline positive. The quantitative results will be used. The definition of negative, indeterminate, and positive is < 8.50 mIU/mL, ≥ 8.50 mIU/mL and < 11.50 mIU/mL, and ≥ 11.50 mIU/mL, respectively. If a result is “indeterminate”, a further assessment or judgement will be performed to determine positive or negative.
- HBeAg-positive participants: the qualitative results at Screening will be used to determine if a participant is HBeAg-positive. In case a participant has a missing qualitative result in screening, the most recent non-missing qualitative result before the first dose of the study intervention will be used. If the qualitative result is not available, then the most recent non-missing quantitative value before the first dose of the study intervention will be used.
- Undetectable HBeAg/HBeAg loss: HBeAg < 0.06 IU/mL.

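### STRIVE SAP endpoint 16 (ALT ≤ ULN by visit) has no baseline condition, so participants already at or below ULN before the first dose can count as achieving it

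*SAP*

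**What the plan says.** **Entry.** SAP 1.2.1 states that study populations II and III "as defined in the Master Protocol will be included in this sub-study". Table 2 gives both the same ALT range, "> ULN and \leq 5x ULN".

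**Endpoint.** SAP 4.4.1 lists endpoint 16 as "Proportion of participants achieving ALT \leq ULN across timepoints in the study". The counts and percentages "will be summarized at each visit by cohort. The two-sided 95% Clopper-Pearson CI will also be calculated across visits for each cohort". The population is set at the top of that section: "The analysis of the following secondary endpoints will be conducted based on the FAS, unless otherwise specified". Nothing further is specified for endpoint 16: no condition on baseline ALT and no confirmation at a second visit.

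**Baseline.** In SAP 4.1, "the baseline value will be defined as the most recent non-missing (scheduled or unscheduled) measurement collected prior to the initial administration of study intervention". Screening may last up to 56 days (SAP 1.2.3), so baseline ALT will normally come from a later sample than the screening ALT.

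**Context.** Table 1 ties the endpoint to the objective of assessing the regimens' effect on ALT. SAP section 5 describes single-arm evaluation with no concurrent control. Cohorts are about 10 (1a, 2a, 3a) or 15 (4a, 5a) participants. SAP section 2 rules out hypothesis testing. Under SAP 4.1, missing response data count as failure.

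**The concern.** The response threshold is the same line that participants had to be above to enter. When people are selected on a high value of a fluctuating measurement, some fall back below the line at the next sample without treatment. Part of that fall may already be visible before the first dose.

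Endpoint 16 does not separate such participants from those who were above ULN at baseline and came down on treatment. A comparative trial would share the effect across arms. Here nothing offsets it, and the Clopper-Pearson interval describes sampling error only. In these cohorts one participant moves the percentage by 1/10 = 10 points or 1/15 = 6.7 points. What is at stake is how a descriptive secondary result is read as evidence of an effect on ALT.

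**Working it through.** **The plan's own figures.** Neither document gives a figure for ALT normalisation, within-person ALT variability or the entry ALT distribution, so there is no ALT figure to reproduce. The power values in SAP Table 6 do reproduce (75.6% for n = 10 and 76.4% for n = 15 at a true rate of 25%), but they concern HBsAg loss and are unaffected.

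**Inputs from the documents.** Entry ALT above 1 and up to 5 × ULN; response ALT ≤ ULN at one visit; cohort sizes 10 and 15.

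**Inputs assumed, not in the documents.** True log ALT is normal across people. Each sample adds independent log-normal within-person noise. Entry rests on one screening value. There is no treatment effect. The grid has source-population median 0.8, 1.0, 1.5, 2.0 or 2.5 × ULN, between-person log-SD 0.4, 0.6 or 0.8, and within-person CV 10, 20, 30 or 40%. That makes 60 scenarios, each with 4 million draws before selection on entry.

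**Step 1: no-effect rate at a single visit.** Over the whole grid it is 0.5% to 44%. Of the 60 scenarios, 31 fall in 5–20%, 17 below and 12 above. By source median:

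| Source median | No-effect rate, single visit |
|---|---|
| 0.8 × ULN | 7–44% |
| 1.5 × ULN | 4–16% |
| 2.5 × ULN | 0.5–9% |

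In this model the Day 1 sample and any later sample are exchangeable, so the same share is expected to be ≤ ULN on Day 1, before any dose.

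**Step 2: mid scenario** (median 1.5 × ULN, log-SD 0.6).

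| Rule | CV 20% | CV 30% |
|---|---|---|
| Single visit, all entrants | 8.1% | 12.0% |
| Single visit, Day 1 ALT > ULN | 4.9% | 7.8% |
| Two consecutive visits, all entrants | 3.6% | 5.2% |
| Two consecutive visits, Day 1 ALT > ULN | 1.6% | 2.5% |

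The second row can be checked by hand. With p the single-visit rate and q the rate of two samples both ≤ ULN, the rate given Day 1 > ULN is (p − q)/(1 − p).
- CV 20%: (0.081 − 0.036)/(1 − 0.081) = 0.045/0.919 = 0.049.
- CV 30%: (0.120 − 0.052)/(1 − 0.120) = 0.068/0.880 = 0.077, against 0.078 simulated; rounding of the inputs accounts for the gap.

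Over the whole grid, the Day 1 restriction alone leaves about 0.3% to 32%.

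**Step 3: what this means in a cohort.**
- Expected number already ≤ ULN on Day 1: 10 × 0.081 = 0.8 to 10 × 0.120 = 1.2 for n = 10; 15 × 0.081 = 1.2 to 15 × 0.120 = 1.8 for n = 15.
- Chance of at least one no-effect participant at a given visit, 1 − (1 − p)^n: for n = 10, 1 − 0.919^10 = 57% and 1 − 0.880^10 = 72%; for n = 15, 1 − 0.919^15 = 72% and 1 − 0.880^15 = 85%.
- For scale, the Clopper-Pearson interval for 1 of 10 is 0.3% to 44.5%, and for 1 of 15 it is 0.2% to 31.9%.

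**The case against.** **The entry rules cannot be checked.** The supplied protocol is THRIVE, which enrols ALT ≤ ULN; the STRIVE sub-protocol and the Master Protocol are not available. THRIVE's own ALT criterion covers the year before screening, so selection on one sample cannot be taken for granted in STRIVE. A required repeat ALT would lower the no-effect rate. This stands, and it is one reason why no single figure can be given.

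**Much is already visible.** Baseline ALT is summarised and listed (SAP 4.2.2), liver tests are summarised with change from baseline (4.7.4.1), and individual ALT is plotted at each visit (4.4.1). Appendix 2 treats Day 1 as an analysis visit for liver tests, so a Day 1 row may already be intended. This stands in part. A careful reader could find the affected participants, but 4.4.1 does not expressly call for the Day 1 count, and none of these outputs alters the reported proportion.

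**The consequence is small.** The endpoint is secondary and untested, the intervals are wide, and missing data count as failure. That is correct. Nor can the no-effect rate simply be subtracted: those who would have fallen back anyway overlap with those who normalise on treatment, and noise also pushes some truly normal values above ULN.

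**A reader might infer that the SAP contradicts itself, because endpoint 12 is conditioned on baseline.** It says "The percentage will be based on those participants who have HBeAg tested positive at baseline in the FAS", but the notes to 4.4.1 set HBeAg status from the screening result, with other pre-dose values only as a fallback. Endpoint 12 needs a restriction because STRIVE also enrols HBeAg-negative participants. It is not a precedent for a Day 1 rule.

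**A reader might infer that a two-visit rule is required.** It would change a per-visit status into a different quantity and, with missing counted as failure, penalise one missed visit. The documents do not call for it.

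**Conclusion.** The structural point holds on the text alone: the response cut-off equals the entry cut-off, baseline is a later sample, and the denominator is the whole FAS. Participants already ≤ ULN before dosing can therefore be counted as achieving ALT ≤ ULN, with no control arm to offset them.

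The size is not established by the documents. Under the assumed grid the no-effect single-visit rate lies between about 0.5% and 44%; the mid scenario gives about 8–12%, or roughly one to two participants per cohort. A reader might be tempted to state 5–20% as the expected rate, but 29 of the 60 scenarios fall outside that band and none of the inputs behind it is in the documents.

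This is a cheap improvement in how a secondary, descriptive endpoint is reported. It does not affect the primary endpoint or the sample size.

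**What to change.** In SAP 4.4.1, for endpoint 16:

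- Report the proportion with ALT ≤ ULN by visit and cohort among FAS participants whose baseline (last pre-dose) ALT is > ULN, with the same interval.
- In the same table, show the number and percentage of each cohort already ≤ ULN at baseline.
- Keep the full-FAS row, so that the statement in SAP section 3 that no FAS participant is excluded from efficacy analysis is still met.
- Optionally, add a two-consecutive-visit version as a supplementary line. It should not replace the per-visit endpoint.

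The restriction reduces regression to the mean but does not remove it, because baseline ALT is itself a noisy value: in the mid scenario the rate falls from 8.1% to 4.9% at CV 20%, and from 12.0% to 7.8% at CV 30%. A table footnote should say so.

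The cost is a few lines of SAP text and one derived flag (two with the optional line), from data already collected. The restricted row has a slightly smaller denominator, about one to two fewer participants per cohort in the mid scenario, and is likely to show a somewhat lower rate.
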